## Introduction

*Helicobacter pylori* (*H. pylori*) infect more than 50% of humans globally. It is the principal cause of chronic gastritis, gastric ulcer, duodenal ulcer, gastric adenocarcinoma and gastric mucosa-associated lymphoid tissue lymphoma (MALToma) [1,2]. In most international guidelines [3-6], standard triple therapy consisting of a proton-pump inhibitor (PPI), clarithromycin and amoxicillin (or metronidazole) for 7 to 14 days is recommended as the choice of treatment for first-line therapy of *H pylori* infection, especially in areas of low clarithromycin resistance (< 15%). Recently, the eradication rates of standard triple therapy have declined to less than 80% in many countries, largely owing to emerging organism resistances [7-10]. Some European studies even reported very poor treatment outcomes of the standard therapy with failure rates of 25-60% [11-13]. Several strategies including sequential therapy, concomitant therapy and hybrid therapy have therefore been proposed to increase the eradication rate [14-16].

Concomitant therapy is another novel regimen proven successful in the presence of clarithromycin resistance [15]. It is a 4-drug regimen containing a PPI (standard dose, b.i.d.), clarithromycin (500 mg, b.i.d.), amoxicillin (1 g, b.i.d.) and metronidazole (500 mg, b.i.d.)

which are all given for the entire duration of therapy. This therapy is superior to standard triple therapy for *H pylori* eradication [17]. It is also less complex than sequential therapy as this regimen does not involve changing drugs halfway through. A head-to-head non-inferiority trial of 10-day sequential and 10-day concomitant therapy showed they were equivalent (93.1% vs 93.0% by per-protocol analysis) [18].

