Recently, we have developed a new anti-*H pylori* regimen — hybrid therapy , which consists of a dual therapy with a PPI (standard dose, b.i.d.) and amoxicillin (1 g, b.i.d.) for 7 days followed by a quadruple regimen with a PPI (standard dose, b.i.d.), amoxicillin (1 g, b.i.d.), clarithromycin (500 mg, b.i.d.) and metronidazole (500 mg, b.i.d.) for 7 days [16]. The novel therapy provided excellent eradication rates of 99% and 97% according to per-protocol and intention-to-treat analysis [16]. Several randomized controlled trials subsequently demonstrated that hybrid regimens were comparable with or more effective than sequential regimens [19-22]. It is important to note that the new therapy has a high efficacy in the treatment of *H pylori* strains harboring dual resistance to clarithromycin and metronidazole. Several studies have shown that sequential therapy is ineffective to clear *H pylori* with dual resistance [14]. The prolonging treatment duration of amoxicillin to 14 days in hybrid therapy might account for the higher eradication rate in the face of *H pylori* stains with dual resistance to clarithromycin and metronidazole. A study from Italy [20] which compared markedly different durations of therapy (14-day hybrid therapy vs 5-day concomitant therapy) showed that 14-day hybrid therapy was superior by PP analysis (95.7% vs 85.1%). However, another

randomized controlled trial showed comparable eradication efficacy between hybrid and concomitant therapies [23]. The study also showed that there was a borderline significant trend toward higher compliance with hybrid therapy compared with concomitant therapy (99% vs 95%) [23]. Many expert recommendations therefore proposed hybrid therapy as a treatment option for *H pylori* in areas with moderate or high clarithromycin resistance [24-27].

Switching drugs halfway through the course increases the complexity of an anti-*H pylori* regimen. Reversing the sequence of drug administration (a quadruple regimen followed by a dual regimen) simplifies hybrid therapy and make it become a one-step two-phase therapy. We recently conducted a multi-center, randomized controlled trial to compare the efficacies of reverse hybrid therapy and standard triple therapy [28]. The data indicated that reverse hybrid therapy achieved a higher eradication rate than standard triple therapy (95.5% vs 88.6%) by ITT analysis.

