### ***Statistical analysis***

The primary outcome variable is eradication rate. The secondary outcome variables are the rate

of adverse events and compliance. Chi-square test with or without Yates correction for continuity and Fisher's exact test are used when appropriate to compare the major outcomes between groups using the SPSS program (version 10.1, Chicago, Illinois, USA). A *P* value less than 0.05 is considered statistically significant.

Eradication rates are evaluated by ITT and per-protocol (PP) analyses. ITT analysis includes all randomized patients who have taken at least one dose of study medication. Patients whose infection status is unknown following treatment are considered treatment failures for the purposes of ITT analysis. The PP analysis excludes the patients with unknown *H. pylori* status following therapy and those with major protocol violations.

To determine the independent factors affecting the treatment response, Host and bacterial parameters are analyzed by univariate analysis. These variables include the following: age (<60 or  $\geq$ 60 years), gender, history of smoking, history of alcohol consumption (<80 g/day or  $\geq$ 80 g/day), ingestion of coffee (<1 cup/day or  $\geq$ 1 cup/day), ingestion of tea ((<1 cup/day or  $\geq$ 1 cup/day), coexistence of a systemic disease (yes or no), previous history of peptic ulcer disease, endoscopic appearance (ulcer or gastritis), CYP2C19 polymorphism, drug compliance (good or poor), and antibiotic susceptibility. Those variables found to be significant by univariate analysis are subsequently assessed by a stepwise logistic regression method to identify independent factors for eradication outcome.

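### The predictor analysis screens 12 factors at P<0.05 and then selects stepwise on about 14 expected failures, so chance factors can be named and modest effects overstated

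*Combined protocol and SAP*

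**What the plan says.** The Abstract and the Introduction give two aims: to compare the regimens, and to find host and bacterial factors that predict outcome. For the second, the Statistical analysis section lists 12 variables: age, gender, smoking, alcohol, coffee, tea, systemic disease, ulcer history, endoscopic appearance, CYP2C19, compliance and antibiotic susceptibility. Each is analysed univariately. Then: "Those variables found to be significant by univariate analysis are subsequently assessed by a stepwise logistic regression method", the purpose being "to identify independent factors for eradication outcome".

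The only significance threshold in the document is P<0.05. For this analysis the plan gives no expected number of failures, limit on model size, multiplicity control, penalisation, validation or exploratory label. It does not name the screening test, say whether regimen is in the model, or state the analysis set. The Abstract's wording can also be read as a separate search within each regimen; the other sections do not settle this.

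**The concern.** The information in a logistic model is limited by the rarer outcome, here failure of eradication, and both regimens are expected to fail seldom. Choosing variables by P-value on few failures has two consequences. Some factors with no effect pass. A real factor passes mainly in samples where chance has enlarged its estimate, so the odds ratio that gets reported tends to be too large. The plan would then present the survivors as independent predictors with nothing to warn the reader. At stake is the reliability of one of the two stated aims.

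**Working it through.** **No figure of the plan to reproduce.** The plan states no failure count or power for this analysis, so the expected failures must be built from the rates it cites.

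**Inputs.** N = 248 (Study population). Allocation is not stated; 1:1 is assumed, 124 per arm. Cited rates, all from the Introduction:
- Reverse hybrid: "reverse hybrid therapy achieved a higher eradication rate than standard triple therapy (95.5% vs 88.6%) by ITT analysis".
- Concomitant, 10-day regimen: "showed they were equivalent (93.1% vs 93.0% by per-protocol analysis".
- 14-day hybrid: "excellent eradication rates of 99% and 97% according to per-protocol and intention-to-treat analysis".
- 14-day hybrid against 5-day concomitant: "14-day hybrid therapy was superior by PP analysis (95.7% vs 85.1".

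**Expected failures** = 124 × (1 − p1) + 124 × (1 − p2):

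| Rates used | Failures | Per candidate (÷12) |
|---|---|---|
| 95.5% and 93.0% | 5.58 + 8.68 = 14.3 | 1.2 |
| 95.5% in both arms | 11.2 | 0.9 |
| 97% in both arms | 7.4 | 0.6 |
| 95.5% and 85.1% | 5.58 + 18.48 = 24.1 | 2.0 |
| 99% in both arms | 2.5 | 0.2 |

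The central figure mixes an ITT rate with a per-protocol rate from a shorter regimen, because no 14-day concomitant rate is cited. The 24.1 uses a 5-day comparator and is an extreme. Separate models by regimen would have about 6 and 9 failures.

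**False factors when nothing has an effect.** Twelve independent tests at exactly 5% would give 1 − 0.95^12 = 46%. Tests on sparse tables are often conservative, so the real figure is lower. Simulation with 12 independent binary factors (assumed prevalences 5-50%), a screen at 0.05 and then forward stepwise selection at an assumed 0.05 names at least one factor, at 14 failures, in:
- 34% of analyses (Pearson, or Fisher if an expected count is below 5);
- 29% (Yates, or Fisher in the same case);
- 22% (Yates throughout).

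The screening step alone gives about 16-39% over 7 to 24 failures and these tests.

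**Inflation of a real factor.** One binary factor, 15% prevalence (assumed), 14 failures, Pearson/Fisher screen:

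| True OR | Median OR when selected | Ratio |
|---|---|---|
| 2 | 4.4 | 2.2 |
| 2.5 | 4.6 | 1.8 |
| 4 | 5.3 | 1.3 |
| 6 | 7.0 | 1.2 |
| 8 | 8.7 | 1.1 |

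The chance of passing the screen is about 30% for a true OR of 2.5, 60% for 4, 82% for 6 and 91% for 8. For a true 2.5, the median selected OR is 6.8 at 7 failures and 3.7 at 24.

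**The alternative, at 14 failures.** With three null factors fixed in advance, at least one reaches P<0.05 in about 11% (Firth, with regimen in the model) or 8% (ordinary tests). For a true OR of 2.5, the Firth estimate has a median of 2.7 over all runs, with 95% coverage. Ordinary logistic regression would have no finite estimate for at least one of the three factors in 14-22% of datasets, hence the sparse-event method.

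**The case against.** - **Selected odds ratios need not be much inflated.** The Introduction attributes the decline of standard triple therapy largely to resistance, so a large resistance effect is plausible here, and at a true OR of 6 to 8 the inflation is only about 10-20%. This stands. A reader might infer that every reported odds ratio will be badly wrong; the true effects are unknown, so the documents do not support that.
- **Chance factors are a risk, not a certainty.** In the full-procedure null simulations over 7 to 24 failures, 63-82% of analyses name no factor. With two real predictors (OR 2.5 assumed) at 14 failures, 68-76% of the factors named are real. It would be wrong to infer that most named factors will be spurious.
- **The screening test is assumed.** A reader might take "Chi-square test with or without Yates correction for continuity and Fisher's exact test are used when appropriate" as the screening rule, but that sentence concerns comparison of the major outcomes between groups. The simulated tests are therefore assumptions, and the range across them matters more than any one value.
- **The analysis set is not stated.** The plan says "Patients whose infection status is unknown following treatment are considered treatment failures for the purposes of ITT analysis". One might infer that the regression is filled with such failures, but nothing says it uses the ITT set, and no dropout rate is given.
- **The remedy's gain comes from testing fewer terms.** Per factor, 11%/3 = 3.7% is no better than 34%/12 = 2.8% or 22%/12 = 1.8%. Nor may the all-runs median of 2.7 be set against 4.6, which is conditional on significance. A similarly corrected estimate restricted to significant results has a median of about 4.7. This stands, and limits what can be claimed for the remedy.
- **It is not a primary or secondary outcome.** True, which limits the severity. It is still a stated aim, and stepwise selection being customary does not make its results reliable.

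**Conclusion.** The concern holds. On the cited rates the plan has about 14 failures for 12 candidates (7 to 24, and as few as 2.5 at the 99% per-protocol rate). If no factor matters, it names at least one in roughly 22-34% of analyses at 14 failures. Surviving odds ratios are about doubled when the true value is 2 to 2.5 and nearly unbiased when it is about 8. These sizes rest on 1:1 allocation, mixed ITT and per-protocol proxy rates, binary factors, assumed prevalences and assumed tests. The conclusion that failures are too few for this kind of selection does not depend on any single one of them.

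A reader might extend the point to the comparison of eradication rates. That does not follow: the comparison is a separate analysis and does not use the selected model. The change should be made, but it concerns the second aim only.

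**What to change.** In the Statistical analysis section:

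1. Delete the univariate screen and the stepwise selection.
2. Fit one pooled logistic model with regimen and about three factors at most, one term each, chosen by the investigators before the data are seen (for example the resistance results and CYP2C19). Use fewer factors if failures are very few, by a rule written in advance.
3. State the population: patients with known *H. pylori* status. Use a method suited to sparse events, such as Firth penalisation.
4. Report every prespecified odds ratio with its 95% CI, significant or not. Tabulate the remaining factors descriptively by arm, and label the analysis exploratory.

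The gain is a lower chance of naming a false factor (about 8-11% against 22-34% at 14 failures) and a report not filtered by significance. A factor singled out because it is significant would still be overstated.

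**Cost.** SAP wording only; no new data. Fewer factors are formally tested. Power for a true OR of 2.5 stays about 30-35%, and a typical CI runs from about 0.7 to 8. Patients without a susceptibility result leave the model: with results in an assumed 80% or 60% of patients, about 11 or 9 failures remain, power is 26% or 22%, and a typical CI is 0.6 to 9 or 0.5 to 11. Software other than the stated SPSS version may be needed.
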